### 8.1. Adverse Events Analyses

SAEs, AEs leading to withdrawal and non-serious ADRs will be collected.

The incidence of any given adverse event (SAE, ADR or non-serious AEs leading to withdrawal) for each treatment group is defined as the proportion of participants in that group who have experienced at least one such adverse event during the study period.

Adverse event (SAE or ADR) summaries including the summary of adverse drug reactions (ADRs), Serious (SAEs) and non-serious adverse events leading to withdrawal of study will be based on GSK Core Data Standards. The details of the planned displays are provided in Section [10.8 Appendix 8: List of Data Displays](#).

Adverse events will be coded using the Medical Dictionary for Regulatory Activities (MedDRA) coding dictionary. The version of MedDRA used in reporting will be noted in a footnote of the AE overview table.

For the standard on-treatment and post-treatment AE tables, the number and percentage of participants with all AEs (regardless of causality) will be summarized for each treatment group by system organ class (SOC) and preferred term (PT). The ordering of the SOCs and the PTs within the SOCs will both be in descending order of total incidence. A SOC will not be presented when the overall incidence for any AE within the particular system is zero. If the total incidence for any two or more AEs is equal, the events will be presented in alphabetical order.

### 8.2. Adverse Events of Special Interest

A comprehensive list of MedDRA terms based on clinical and safety review will be used to identify AEs of special interest to FF and Relvar/Breo. Changes to the MedDRA dictionary may occur between the start of the study and the time of reporting and/or emerging data from on-going studies may highlight additional AEs of special interest; therefore, the list of terms to be used for each event of interest and the specific events of interest will be based on the clinical and safety review agreements documented and in place at time of reporting and prior to unblinding the study. The details of the planned displays are provided in Section [10.8 Appendix 8: List of Data Displays](#).

The number and percentage of participants with on-treatment AEs of special interest will be summarized for each treatment group by special interest term, subgroup and PT. The ordering of the special interest terms, the subgroups and the PTs within them will all be in descending order of total incidence. If the total incidence for any two or more AEs is equal, the events will be presented in alphabetical order. This summary will be produced for non-serious ADRs, and repeated for serious ADRs, all ADRs and SAEs. The list of MedDRA terms used to identify AEs of special interest will be displayed.

### **8.3.      Pregnancy**

Any pregnancies reported during the study will be summarized in CSR case narratives. Any pregnancy complication or elective termination of a pregnancy for medical reasons will be recorded as an AE or SAE and included in summaries and listings of AEs/SAEs.

### **8.4.      Other Safety Measures**

All Relvar/Breo ELLIPTA inhaler device malfunction data for participants reporting at least one inhaler malfunction will be listed.

## 10. APPENDICES

### 10.1. Appendix 1: Schedule of Activities

#### 10.1.1. Protocol Defined Schedule of Events

Procedures	Screen	Run-In			Treatment Period						EW	Follow -up	Notes
Visit/Contact	V1	V2	V3	V4	V5	V6	V7	V8	V9	V10		V11	
Month of Study	-1	0	0	0	1	2	3	4	5	6			
Day of Study	-28	0	0	0	28	56	84	112	140	168		175	
Visit Window (days)		±2	±2	±2	±2	±7	±7	±7	±7	±7		±2	
Conditional Visits			X	X		X	X	X	X				
SCREENING ASSESSMENTS													
Written Informed Consent	X												Signed by the participant and HCP/ designee prior to any other study assessments. May be completed at a separate visit to screening if required.
Participant Demography	X												
Medical History	X												
Asthma History	X												Including exacerbation history for previous 12 months and those involving hospitalisation
Therapy History	X												Maintenance therapy over previous 12 months, including number of prescriptions requested or provided
Physical Exam	X												Full physical including height, weight and vital signs
Inclusion/Exclusion Criteria	X	X	X	X									ACT assessment for inclusion required at run-in visits
Randomisation		X	X	X									Participant randomised to treatment at only one of V2, V3 or V4 once ACT criteria is met

Procedures	Screen	Run-In				Treatment Period					EW	Follow -up	Notes
Visit/Contact	V1	V2	V3	V4	V5	V6	V7	V8	V9	V10		V11	Conditional Visits: V3 & V4 are only required if a participant is not included at prior run in visit. V6, V7, V8 & V9 are only required for Treatment arms 1 & 3. Randomisation to treatment arms will occur at Visit 2,3 or 4 when randomisation criteria have been met
Month of Study	-1	0	0	0	1	2	3	4	5	6			
Day of Study	-28	0	0	0	28	56	84	112	140	168		175	
Visit Window (days)		±2	±2	±2	±2	±7	±7	±7	±7	±7		±2	
Conditional Visits			X	X		X	X	X	X				
SAFETY ASSESSMENTS													
Concomitant Medication		X											
Urine Pregnancy Test	X	X	X	X	X					X	X		
SAEs	X		X										
Non-Serious Adverse Events that leads to withdrawal	X		X										Non-serious adverse events that leads to dose modification, drug discontinuation, or withdrawal from the trial. Collected from start of run in
Non-serious Adverse Drug Reactions	X		X										Collected from start of run in
Exacerbations	X		X										Severe Exacerbation are to be reviewed and recorded. Collected from start of run in
Unscheduled HCP visits			X										All secondary care contacts and all primary care contacts related to Asthma
QUESTIONNAIRES & Patient Reported Outcomes (PROs) (Performed in the order given here)													
ACT	X	X	X	X	X					X	X		ACT performed at V2, V3 or V4 to confirm inclusion for randomisation
ASUI	X 	X 	X 	X 	X					X	X		1. PRO's only performed at screening once a participant is included. 2. The PRO's are only performed at the run-in visit (V2, V3 or V4) if a participant is randomised to treatment
SGRQ		X 	X 	X 	X					X	X		
PAM	X 	X 	X 	X 	X					X	X		
MARS-A	X 	X 	X 	X 	X					X	X		
BMQ	X 	X 	X 	X 	X					X	X		
EXIT Questionnaire										X	X		

Procedures	Screen	Run-In				Treatment Period					EW	Follow-up	Notes
Visit/Contact	V1	V2	V3	V4	V5	V6	V7	V8	V9	V10		V11	Conditional Visits: V3 & V4 are only required if a participant is not included at prior run in visit. V6, V7, V8 & V9 are only required for Treatment arms 1 & 3. Randomisation to treatment arms will occur at Visit 2,3 or 4 when randomisation criteria have been met
Month of Study	-1	0	0	0	1	2	3	4	5	6			
Day of Study	-28	0	0	0	28	56	84	112	140	168		175	
Visit Window (days)		±2	±2	±2	±2	±7	±7	±7	±7	±7		±2	
Conditional Visits			X	X		X	X	X	X				
Exit Interview											X	X	X
ASSESSMENTS													
Fractional exhaled Nitric Oxide (FeNO)	X 	X 	X 	X 	X						X	X	1.PEF & FeNO only performed once a participant is included. 2.PEF and FeNO is only performed at the Run-in visit if a participant is randomised FeNO performed prior to PEF
Peak Expiratory Flow (PEF)	X 	X 	X 	X 	X						X	X	
HCP dashboard review					X	X	X	X	X	X			Participants in treatment arms 1 and 3 only. HCP will record action and outcome of review.
INVESTIGATIONAL PRODUCT													
Dispense Sensors	X												Sensors must be attached and switched on in clinic.
Dispense Relvar/Breo ELLIPTA	X	X											All participants will attend independent dispensing visits to collect their next Relvar/Breo ELLIPTA and/or salbutamol MDI as required. Patients are required to bring the sensor to the dispensing visits. The sensor will be attached to the new device and switched on at the dispensing visit.
Dispense Salbutamol MDI	X	X											
Training in CIS	X	X	X	X	X								Participants are trained in fitting the sensors at screening. Following randomisation, participants will be trained in CIS as relevant for their treatment arm. Retraining can be provided at V5.

Procedures	Screen	Run-In			Treatment Period						EW	Follow -up	Notes
Visit/Contact	V1	V2	V3	V4	V5	V6	V7	V8	V9	V10		V11	Conditional Visits: V3 & V4 are only required if a participant is not included at prior run in visit. V6, V7, V8 & V9 are only required for Treatment arms 1 & 3. Randomisation to treatment arms will occur at Visit 2,3 or 4 when randomisation criteria have been met
Month of Study	-1	0	0	0	1	2	3	4	5	6			
Day of Study	-28	0	0	0	28	56	84	112	140	168		175	
Visit Window (days)		±2	±2	±2	±2	±7	±7	±7	±7	±7		±2	
Conditional Visits			X	X		X	X	X	X				
Training in ELLIPTA & MDI correct use	X				X								Once included a participant should be trained in correct use of ELLIPTA and MDI devices
Correct Use Assessment for ELLIPTA and MDI	X				X								Inhaler use technique will be assessed for correct use. This need only be recorded in source.
Return Sensors											X	X	
Return Relvar/Breo ELLIPTA		X									X		Patients are required to return their devices at the independent dispensing visits. Doses remaining on each returned ELLIPTA inhaler will be recorded.
Return Salbutamol MDI		X									X		Patients to return used MDI at dispensing visits.

## 10.2. Appendix 2: Assessment Windows

### 10.2.1. General

Clinic visits are scheduled to take place as specified in [Appendix 1](#): Schedule of Activities. Individual measurements will be reported based on the visits they are assigned to in the study database without adjustment. Measurements outside visit windows will not be excluded from analyses.

If a circumstance should arise where multiple measurements have been collected and recorded against the same timepoint, then the first valid value will be used for that timepoint.

The maximum value obtained from the multiple PEF and FeNO assessments at a visit will be used in summaries and analyses. Participants who withhold a daily dose of maintenance therapy and rescue medication for 6 hours prior to the assessment will have value included in the summaries.

### 10.2.2. Definitions of Assessment Windows for Adherence and Rescue Medication Use Analyses

All participants have a sensor on their maintenance and rescue medication to consistently measure their adherence to maintenance and level of rescue medication use in the study. The sensors are attached to participants ELLIPTA Relvar/Breo maintenance treatment and MDI rescue medication from start of Visit 1 until Visit 10. The sensors record the time and date when the Relvar/Breo ELLIPTA cover is opened and closed and the salbutamol MDI rescue medication is actuated.

Study day 1 is defined as the day of randomisation. This could be the day of Visit 2, 3 or 4, dependent on the length of the run-in period. Study day for all other visits, assessments and events are calculated relative to this.

The following information in [Table 5](#) displays which sensor records are summarised for each analysis time period (Analysis Month). Any sensor data recorded post the Month 6 (day 168) time period will not be included in the analysis of ELLIPTA adherence or salbutamol MDI rescue medication use of sensor data.

**Table 5 Sensor Data Assessment Windows**

Sensor Data Assessment Windows		
Analysis Month	Analysis Period	
	Beginning Timepoint	Ending Timepoint
Baseline	Latest of either Day -28 or day after Visit 1 (minimum of 14 days must be present to create a baseline)	Day -1 (Day prior to randomisation)
1	Day 1 (Day of randomisation)	Day 28 or discontinuation from adherence/rescue assessment if within month 1
2	Day 29	Day 56 or discontinuation from adherence/rescue assessment if within month 2
3	Day 57	Day 84 or discontinuation from adherence/rescue assessment if within month 3
4	Day 85	Day 112 or discontinuation from adherence/rescue assessment if within month 4
5	Day 113	Day 140 or discontinuation from adherence/rescue assessment if within month 5
6	Day 141	Earliest of either day of visit 10, Day 168 or discontinuation from adherence/rescue assessment if within month 6 if participant is a completer  OTHERWISE  Day 168 or discontinuation from adherence/rescue assessment if within month 6
Note: 'Discontinuation from adherence/rescue assessment' occurs at the earliest of premature discontinuation from use of the ELLIPTA /MDI sensor, premature discontinuation of ELLIPTA (for adherence measures), or premature withdrawal from the study.		

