### **Screening Visit (V1)**

Subjects who have provided their informed consent will be screened at Visit 1 (V1) for inclusion on the study. Subjects who meet all the inclusion criteria, including an ACT of <20, will enter the flexible run-in period. Screening and starting the flexible run-in can occur at the same visit, however for logistical reasons the flexible run-in can start at a separate visit, which must be within 7 days of the screening visit and the subject's inclusion on the study. Should a subject not meet the inclusion/exclusion criteria, they will be registered as a screen failure.

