## **9.1. Efficacy Assessments**

### **9.1.1. Primary, Secondary and Other Adherence Measures**

The Primary, Secondary and Other adherence endpoint (adherence to maintenance medication) data is collected by the Clip-on Sensor for ELLIPTA and records the time and date when the ELLIPTA cover is opened and closed.

The sensor will be attached to subjects ELLIPTA Relvar/Breo treatment from start of run-in until V10. References and material for fitting the sensors, downloading the app and other aspects of using the CIS are included in the SRM.

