## **5.2. Baseline Definitions**

Baseline adherence will be the percentage of ELLIPTA doses taken (daily adherence) during the last 28 days of the run-in period prior to randomisation. This will be determined using the randomisation date. A minimum of 14 run-in days prior to randomisation will be required to determine baseline adherence otherwise it will be set to missing. Any missing intermittent daily adherence data will be imputed as non-adherent i.e. the participant will be assumed to have not taken their treatment within the 24-hour time period/window, where there is no evidence of a medical device incident having occurred. Missing data due to a medical device incident such as,

- device failure
- technical failure of the ELLIPTA maintenance sensor
- data transmission failure,

will be assumed to be missing at random (MAR). For each participant the baseline percentage adherence measure will be calculated as the number of days a participant is adherent divided by the number of days without medical device incident within the baseline assessment period \* 100. See Section [10.2.2](#) Definitions of Assessment Windows for Adherence and Rescue Medication Use Analyses, for the definition of the baseline assessment period.

Baseline rescue free days will be the percentage rescue free days (RFDs) during the last 28 days of the run-in period prior to randomisation. This baseline will be determined in the same manner as the adherence baseline.

Where baseline assessments are determined from the randomisation visit, no unscheduled assessments will be considered as the baseline value.

Where baseline assessments are determined from the screening visit, Visit 1 will be used and no unscheduled screening visits will be considered as the baseline value.

If time is not collected, Day 1 assessments are assumed to be taken prior to first dose and used as baseline.

Parameter	Study Assessments Considered as Baseline			Baseline Used in Data Display
	Visit 1 Screening	Study Days -28 to -1	Randomisation Visit, Study Day 1 (Pre-Dose)	
Efficacy				
ELLIPTA Adherence Endpoints (%)		x		% adherence from Day -28 to Day -1
Rescue Free Days (RFDs) (%)		x		% RFDs from Day -28 to Day -1
Total Rescue Use (TRU) (puffs)		x		Total use from Day -28 to Day -1
ACT Total score			x	Randomisation
SGRQ Total score			x	Randomisation
ASUI Total score			x	Randomisation
PAM-13 Total score	x			Screening
BMQ Total score	x			Screening
MARS-A Total score	x			Screening

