### 10.5.3.2. MDI Device Sensor Assessments

[figure not shown]
Percentage of Rescue Free Days Endpoint
Overview of Calculation

 
1. Create a dataset (Observed Data A) to calculate the monthly observed percentage of MDI rescue free days values (from month 1 to month 6) accounting for the following,             
 
a. number of days MDI rescue medication was used (at least once per day)
 
b. number of days post MDI rescue use sensor permanent discontinuation
 
c. the intermittent missing daily MDI rescue use data due to device incident
 
d. MDI Rescue free days (i.e. none of the above).
 
 
 
2. Duplicate the observed monthly MDI rescue free values dataset (Observed Dataset A). Using the values in the duplicate dataset (Dataset B), impute the month where the sensor was permanently discontinued before the end of that month (and therefore presents a monthly adherence rate based on partly observed sensor data for that month) as missing unless the participant is a study completer.
 
3. Using each of the two observed datasets (Observed Dataset A and Observed Dataset B), create four separate imputed datasets (J2R-Dataset A, J2R-Dataset B, MAR-Dataset A, MAR-Dataset B) that account for the two imputation methods (J2R or MAR) that may be applied to participants data after discontinuation of the MDI rescue sensor or withdrawal from study. Imputation will be carried out using observed monthly MDI rescue free rates for months 1 to 6. 1000 draws will be used. Completely missing intermediate monthly values will be assumed MAR. The multiple imputation will be implemented using the methods described in Carpenter, 2013, using the macros (Part1A, Part1B, Part2A and Part2B) available from https://missingdata.lshtm.ac.uk/2017/04/06/qsk-five-macros/ using seeds documented in the RAP for the respective endpoint.
 
4. The Observed Datasets (A and B), imputed datasets (J2R-Dataset A, J2R-Dataset B, MAR-Dataset A, MAR-Dataset B) and the timing of the intercurrent events; permanent discontinuation of the MDI rescue sensor and withdrawal from study; will be used to create an analysis dataset (Dataset C) that identifies the proportion of each month to be assigned as observed data, J2R imputed data or MAR imputed data. The strategy for handling intercurrent events is described in Section 7.2.2.3 Strategy for Intercurrent (Post-Randomisation) Events.  Within each imputation draw, for each missing month, the observed and any imputed data will be combined to provide a percentage of rescue free days value. The values for months 4 to 6 will be combined to create the value for the respective secondary endpoint analysis and the weight to be assigned to each participant.
 
5. Analyse using Multiple Imputation macro Part3
 

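### The baseline sensor window is anchored to Visit 1, but the protocol lets sensors start up to 7 days later; as written, sensor-free days can count as non-adherent and rescue-free

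*SAP*

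**What the plan says.** **Start of the window.** The Baseline row of SAP Table 5 begins at "Latest of either Day -28 or day after Visit 1 (minimum of 14 days must be present to create a baseline" and ends the day before randomisation. SAP 10.2.2 says the sensors are on the inhalers "from start of Visit 1 until Visit 10".

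**Start of the sensors.** Protocol 5.1 (Screening Visit) says that "for logistical reasons the flexible run-in can start at a separate visit, which must be within 7 days of the screening visit". Protocol 6.4 treats the run-in as entered once run-in medication is dispensed. Protocol 9.1.1 says: "The sensor will be attached to subjects ELLIPTA Relvar/Breo treatment from start of run-in until V10". Section 9.1.2.2 says the same of the MDI sensor.

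**Definition of baseline.** SAP 5.2 defines baseline adherence over the last 28 days of the run-in and requires at least 14 run-in days. It then refers to 10.2.2 for the assessment period itself. It also says: "Any missing intermittent daily adherence data will be imputed as non-adherent", unless there is evidence of a device incident.

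**Classes of day.** Step 1 of SAP 10.5.3.1 and 10.5.3.2 sorts every day in the window into four classes: use recorded (D1), device incident (D2), after sensor discontinuation (D3), and a remainder (D4). D5 is their sum. For ELLIPTA the remainder is non-adherent. For the MDI it is "MDI Rescue free days (i.e. none of the above").

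**The concern.** The Visit 1 limb of Table 5 looks like a guard against counting days before a sensor was in place. It works only when screening and dispensing fall on the same day. After a deferred start, the window can include days with no study inhaler and no sensor. Such days are neither device incidents nor days after discontinuation, and no class exists for a sensor that has not yet been activated. They drop into D4, which lowers baseline adherence and raises baseline rescue-free days. In baseline total rescue use they contribute zero puffs.

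Baseline adherence is a covariate in the primary ANCOVA, the secondary adherence models and the GLM sensitivity analysis. It also falls within the treatment-by-covariate interaction tests at the 10% level. Baseline rescue-free days is a covariate in the rescue-free-day model. At stake are the quality of these covariates and the accuracy of the baseline tables.

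**Working it through.** **The plan's own figure.** The documents give no number for this point. The design power in protocol 11.2.1 reproduces: with 76 per arm, difference 15 and SD 28, power = Φ(15 / (28·√(2/76)) − 1.96) = Φ(3.30 − 1.96) = 0.910, against a stated value of about 90%. It uses no baseline covariate, so this point does not alter it.

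**Inputs.**
- Day numbering (SAP 10.2.2, 10.5.1): "Study day 1 is defined as the day of randomisation", and there is no Day 0. If V1 is d days before randomisation, V1 is Day −d.
- Run-in starts k days after V1, with k from 0 to 7 (protocol 5.1), so dispensing is on Day −d + k.
- V2 has a window of ±2 days (Schedule of Activities). The Schedule puts V1 at Day −28, which suggests timing V2 from V1. The text of protocol 5.1 puts V2 at the end of a run-in month, which suggests timing it from the run-in start.

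**Formulas.**
- Window start s = max(−28, −d + 1); window length n = −s.
- Sensor-free days = max(0, (−d + k) − s). The dispensing day itself is not counted as lost.
- Recorded value for perfect adherence = (n − lost) / n.

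**Results, randomised at V2 with k = 7.**

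| V2 timed from | Interval | d | n | Lost | Perfect adherence recorded as |
|---|---|---|---|---|---|
| V1 | 26 days | 26 | 25 | 6 | 19/25 = 76.0% |
| V1 | 28 days | 28 | 27 | 6 | 21/27 = 77.8% |
| V1 | 30 days | 30 | 28 | 5 | 23/28 = 82.1% |
| Run-in start | 26 days | 33 | 28 | 2 | 26/28 = 92.9% |
| Run-in start | 28 days | 35 | 28 | 0 | 100% |
| Run-in start | 30 days | 37 | 28 | 0 | 100% |

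Timed from V1 with k = 3, the loss is 2 of 25, 2 of 27 or 1 of 28 days. A deferral of 0 or 1 day has no effect. For V3 or V4, Day −28 falls after dispensing, so nothing is lost.

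**Other levels (timed from V1, d = 28, k = 7).**
- The two group means quoted in protocol 11.2.2: 66% becomes 66 × 21/27 = 51.3%, and 88% becomes 68.4%.
- Rescue-free days at assumed true values of 30%, 50% and 70% become 45.6%, 61.1% and 76.7%; for example, (6 × 100 + 21 × 50)/27 = 61.1%.
- Someone who uses rescue every day is recorded as 6/27 = 22.2% rescue-free instead of 0%.

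**Cost in precision, as an illustration.** This simulation assumed a correlation near 0.80 between baseline and outcome, everyone randomised at V2 timed 28 days from V1, and deferrals spread evenly over 1 to 7 days. The residual SD rises by 0.9% if 10% of participants are deferred, 2.4% if 30% are, and 4.1% if all are. Mean recorded baseline falls from 66.7% to 66.0%, 64.5% and 59.3% respectively.

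**The case against.** The best defence is SAP 5.2. It speaks of the run-in period and of run-in days, and under protocol 6.4 a day before dispensing is not a run-in day. A programmer who followed 5.2 alone would leave those days out. Its imputation rule also covers intermittent gaps, which days before first dispensing are not. This stands to the extent that the miscount is not certain. But 5.2 hands the definition of the window to 10.2.2, and SAP 10.3.1 elsewhere dates the run-in from the screening visit when phasing medications, exacerbations and adverse events. The documents conflict, and the operative table is on the wrong side.

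The second defence is the sensor synchronisation dates, which Step 1 uses to classify missing observations. That use is stated only for malfunction, with no rule for days before the first synchronisation. Protocol 5.1 describes app and home-hub set-up after randomisation, so the first synchronisation might not mark dispensing. The connection details are in a manual that is not available here, so neither reading can be confirmed.

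Third, the Schedule of Activities shows sensors and ELLIPTA dispensed at V1, so the SAP wording has a source in the protocol and the tension begins there. The larger losses also need the full 7-day deferral together with V2 timed from V1, which means a run-in of only 19 to 23 days (d − k) where the text speaks of a month. This stands, and it is why the lower range must be given equal weight.

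A reader might infer that the treatment comparison is biased. The documents do not support that: the window closes before randomisation and allocation is central, so deferral cannot depend on arm.

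**Conclusion.** The passages conflict, and Table 5 applied literally gives a wrong baseline for participants randomised at V2 after a deferred run-in start. The error is 0 to 2 of 28 days if V2 follows the run-in start, and up to 5 to 6 of 25 to 28 days if V2 is timed from V1 with a 7-day deferral. The documents support both timings and do not say how often deferral occurs, so the overall effect cannot be fixed from them.

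The consequence is limited to noisier covariates in the adherence and rescue-free-day models and misstated baseline tables. The arm contrast is not biased, and stated power and sample size do not change. It would go too far to say that every sensor-free day will be miscounted, since SAP 5.2 and the synchronisation check leave room for correct programming. The change is still worth making, because the rule as written yields a wrong value and the correction is nearly free.

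**What to change.** - In Table 5 and SAP 5.2, start the baseline window at the later of Day −28 and the day after that sensor's first activation date, separately for the ELLIPTA and MDI sensors. The activation date is already collected (listing shells SAFE_L2 and SAFE_L3).
- Apply the 14-day minimum to days after activation. In the worst in-window cases (k = 7, V2 timed from V1) d − k − 1 full days remain: 18, 20 or 22 for d = 26, 28 or 30. No in-window baseline is lost.
- Reconcile SAP 10.2.2 with the protocol, which attaches sensors from the start of the run-in.
- Report baseline total rescue use with the number of contributing days, or as a daily rate. Moving the window start does not change a sum to which the dropped days add zero.

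The cost is one SAP rule and its programming, with no new data. It should be settled before the treatment codes are released.
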